Study Product, Dose, Route, Regimen	TWB-103, allogeneic human fibroblasts + gelatin-based hydrogel, applied 2 to 3 times till 100% re-epithelialization or up to 10 days (around once every 3 days); a matching placebo, freezing solution with gelatin-based hydrogel, is used as the control and applied to patients in the same duration and dosing frequency as TWB-103.
Duration of Treatment	During the planned treatment period (14 days), each patient will receive TWB-103+Tegaderm™ or placebo+Tegaderm™ for up to 10 days or to the day of 100% re-epithelialization, whichever comes first, followed by Tegaderm™ alone application from Day 10 to Day 14 if failing to achieve 100% re-epithelialization by Day 10.
Study Visits	
Patients will be scheduled to attend the following visits:
 
1. Screening (within 2 weeks prior to DSW creation)2. Day 0 (treatment begins)3. Day 3 (\pm 1 day)4. Day 7 (\pm 1 day)5. Day 10 (\pm 1 day)6. Day 14 (\pm 2 days, end of treatment)7. Day 28 (\pm 3 days, Follow-up)8. Day 42 (\pm 3 days, Follow-up)

9. 90 ± 14 days after Visit 7 or Visit 8 (Follow-up)

10. 180 ± 14 days after Visit 7 or Visit 8 (Follow-up)

11. 270 ± 14 days after Visit 7 or Visit 8 (Follow-up)

12. 360 ± 14 days after Visit 7 or Visit 8 (Follow-up)

Note: (1) For patients with complete wound closure by Day 14, the confirmation of wound closure will be assessed on Day 28.

(2) Day 42 follow-up is only scheduled when the wound closure is not completed by Day 14 but is observed on Day 28. The wound closure will be re-confirmed on Day 42.

(3) If no Visit 8, Visit 9~12 should be scheduled following Visit 7.

(4) In case patients achieve 100% re-epithelialization before or at Day 10, patients will finish up the assessments on the day with 100% re-epithelialization. This day of 100% re-epithelialization will be the end of treatment and the remaining scheduled treatment visits, if applicable, will be dismissed.

Patient Assignment Patients who meet all eligibility requirements for entry into the study will be randomized into one of the treatment group or control group in 1:1 ratio as shown below:

Treatment Group:

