11. When patients are withdrawn from the study by Day 28, they are required to finish all assessments of Day 28, except the application and dispensation of TegadermTM. The unused TegadermTM should be returned if received from the previous visit. For patients who have initially scheduled Day 42 visit but make the decision between Day 28 to Day 42 to withdraw from the study, he/she should be encouraged to complete assessments planned for Day 42 visit at the earliest date convenient for the patients. If patients have entered the long-term follow-up period (i.e. after Day 28 or Day 42 if scheduled) and the decision of withdrawal is confirmed, effort must be made to understand and record the reason of withdrawal.
12. In case patients achieve 100% re-epithelialization before or at Day 10, patients will finish up the assessments on the day with 100% re-epithelialization. This day of 100% re-epithelialization will be the end of treatment and the remaining scheduled treatment visits, if applicable, will be dismissed.
13. When patients experience > Grade 2 skin allergic reaction or > Grade 2 systemic allergic reaction related to the product/placebo or develop infection that the continuation of TWB-103/placebo is considered inappropriate at the investigator's discretion, patients should finish the scheduled assessments (except that application of TWB-103/placebo is stopped; that the application and dispensation of TegadermTM will be at the investigator's discretion; and that the return of TegadermTM will be asked if applicable) and will continue the remaining visits (application of TWB-103 or placebo will be stopped if planned originally).
14. When unscheduled visits are requested, patients should finish the assessments of Day 14 (except that the completion of hemogram and serum biochemistry as well as the application and dispensation of TegadermTM will be at the investigator's discretion; and that the return of TegadermTM is not required) during the unscheduled visit. The option to choose Vaseline Gauze or Non-Stick Gauze such as silastic foam dressings only can be selected on or after Day 14.
15. When the first 100% re-epithelialization is not observed by Day 28, the DSWs will be followed till 100% re-epithelialization.

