2.2 Endpoints

2.2.1. Primary endpoints

The primary endpoint for this study is:

Phase I

Safety:

Incidence of treatment-related AEs and SAEs (including infections and bleeding)

Phase I+II

Efficacy:

The healing time from DSW creation to the first 100% re-epithelialization with confirmation for at least 10 days apart, assessed by the investigator

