3.4 Withdrawal Criteria

Patients may be withdrawn from the trial due to any of the following conditions:

1. The patient decides to withdraw her/his informed consent form.
2. Investigator considers that the patient is no longer physically and/or psychologically feasible to remain in the study.
3. The patient refuses to proceed with critical measures for the study endpoints, defined as all variables required for primary endpoint evaluation.
4. The patient has lost to follow-up

The reasons for discontinuation must be recorded in the Case Report Form (CRF) and in the patient's medical records for all early terminated cases. All study participants withdrawn from the study before Day 28 will finish assessments of Visit 7 (Day 28), except the application and dispensation of TegadermTM. If the patient has received TegadermTM from the visit before withdrawal, the return of TegadermTM should be made. For patients who have initially scheduled Day 42 visit but make the decision between Day 28 to Day 42 to withdraw from the study, he/she should be encouraged to complete assessments planned for Day 42 visit at the earliest date convenient for the

patients. If patients have entered the long-term follow-up period (i.e. after Day 28 or Day 42 if scheduled) and the decision of withdrawal is confirmed, effort must be made to understand and record the reason of withdrawal. If a patient is discontinued due to an AE, every effort will be made to follow the event until resolution.

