10.2.2 Analysis methods

For all assessments, the baseline will be defined as the most recently available data before the administration of 1st dose treatment.

Descriptive statistics will be provided by treatment group/country and by all for all of the endpoints, including primary and secondary ones. Frequency table will be provided for categorical data, while mean, standard deviation, maximum, minimum, median, inter-quartile range (IQR), and 95% two-sided confidence interval will be calculated for continuous measurements.

AEs and SAEs will be reported by treatment group/country and physiological systems as appropriate. The incidence of treatment-related AEs and SAEs between treatments will be analyzed by Cochran-Mantel-Haenszel test (CMH) test.

Incidence of AEs and SAEs will be analyzed by CMH test. Changes in physical examinations will be displayed for each individual system. Net changes from pre-treatment laboratory test results and vital signs will be analyzed by descriptive statistics.

Healing time from DSW creation to 100% re-epithelialization will be estimated by using Kaplan-Meier methods and compared between groups by using log-rank test. The healing time is defined as from DSW creation to the first 100% re-epithelialization with confirmation for at least 10 days apart, observed by the investigator and the first additional evaluator.

If the first 100% re-epithelialization is observed at any visit by Day 28 with confirmation for at least 10 days apart, the healing time is noted as the duration from the Day of DSW creation to the day of the first 100% re-epithelialization. The fulfilling of the visits and/or follow-ups after the 100% re-epithelialization date will not be taken into account to determine the healing time. If the 100% re-epithelialization is not observed by Day 28 visit, the healing time will be censored on day of the last visit up to Day 28 visit. If the 100% re-epithelialization is observed by Day 28 visit but no confirmation is made, the healing time will be censored on day of the last visit up to Day 28 visit. The censoring rules will be applied immediately once patients leave the study regardless the participation and/or completion of the long-term (360 days) follow-ups.

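### A patient first seen closed on Day 28 who withdraws before Day 42 is asked for an exit check that can come too early to confirm closure

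*Combined protocol and SAP*

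**What the plan says.** **Endpoint.** Section 2.2.1 defines the primary efficacy endpoint as "The healing time from DSW creation to the first 100% re-epithelialization with confirmation for at least 10 days apart, assessed by the investigator". Section 10.2.2 repeats the condition for counting an event: "If the first 100% re-epithelialization is observed at any visit by Day 28 with confirmation for at least 10 days apart".

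**Unconfirmed closure.** Section 10.2.2 continues: "If the 100% re-epithelialization is observed by Day 28 visit but no confirmation is made, the healing time will be censored". The censoring day is that of the last visit up to the Day 28 visit. It adds: "The censoring rules will be applied immediately once patients leave the study".

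**Who has a Day 42 visit.** The Protocol Summary (Study Visits, note 2) states: "Day 42 follow-up is only scheduled when the wound closure is not completed by Day 14 but is observed on Day 28". Its stated purpose is to re-confirm closure.

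**Withdrawal between the two visits.** Section 3.4, and note 11 of the Schedule of Assessments in the same terms, provide: "For patients who have initially scheduled Day 42 visit but make the decision between Day 28 to Day 42 to withdraw from the study", then "he/she should be encouraged to complete assessments planned for Day 42 visit at the earliest date convenient for the patients". Neither place sets a minimum interval from the closure visit.

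**Withdrawal by Day 28.** Note 11 has a separate rule: "When patients are withdrawn from the study by Day 28, they are required to finish all assessments of Day 28". It gives no date for those assessments.

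**The concern.** The withdrawal instruction and the endpoint definition pull in opposite directions. The endpoint needs the second look to be late enough. The instruction asks for it to be early, and it is the only timing guidance a site receives for these patients. A patient can therefore attend, be seen with a closed wound, and still be censored because of when the site was told to bring the patient in.

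Nothing later repairs the loss. Visits 9 to 12 do not record 100% re-epithelialization (Section 6.11), and Section 10.2.5 rules out imputation. This censoring falls only on patients already observed to have healed, so it is related to the outcome. In a trial planned for 15 evaluable patients per arm, a single event is visible in the Kaplan-Meier estimate at Day 28.

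**Working it through.** The plan has no calculated figure to reproduce here: Section 10.1 calls the sample size arbitrary. The check is a count of days.

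**Inputs from the documents.** Confirmation gap of at least 10 days (2.2.1, 10.2.2). Visit 7 on Day 28 ± 3 (7.5.1) and Visit 8 on Day 42 ± 3 (7.5.2). About 36 recruited for 30 evaluable, 1:1 (3.1).

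**Step 1: earliest valid check.** Earliest day = closure visit day + 10.
- Nominal: 28 + 10 = Day 38.
- Across the Visit 7 window: 25 + 10 = Day 35 to 31 + 10 = Day 41.

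**Step 2: one record.** Closure is first seen on Day 28, the decision to withdraw is made on Day 32, and the exit check is on Day 33 with the wound closed. Gap = 33 − 28 = 5 days, below 10. Closure is unconfirmed and healing time is censored at Day 28.

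**Step 3: how often the check is too early.** Let the decision fall x days after Day 28, with x = 1 to 13, and let the check follow d days later. The check is too early if x + d < 10. With all 13 values of x equally likely (assumption), the share is (9 − d)/13 for d from 0 to 9:

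| Delay d (days) | Share too early |
|---|---|
| 0 | 9/13 = 69% |
| 1 | 8/13 = 62% |
| 2 | 7/13 = 54% |
| 3 | 6/13 = 46% |
| 5 | 4/13 = 31% |
| 7 | 2/13 = 15% |
| 9 or more | 0% |

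Sensitivity with d = 0:
- Decisions weighted towards early days (weights 14 − x): 81/91 = 89%.
- Decisions weighted towards late days (weights x): 45/91 = 49%.
- Even spread, averaged over all 49 combinations of the Visit 7 and Visit 8 windows: 72%.

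**Step 4: comparison with visits kept on schedule.** Over the same 49 window combinations the gap runs from 8 (Day 31 to Day 39) to 20 days. It is under 10 in 3/49 = 6%. The withdrawal instruction is therefore a different and larger source of short gaps than the windows.

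**Step 5: how many patients.** The documents give neither the proportion first closing between Day 14 and Day 28 nor the proportion of those who withdraw before Day 42. Assume 20% to 60% and 5% to 16.7% respectively, with d = 0 and decisions evenly spread:
- Low: 36 × 0.20 × 0.05 × 9/13 = 0.25 patients.
- High: 36 × 0.60 × 0.167 × 9/13 = 2.5 patients.

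**Step 6: weight of one lost event.** With 15 in an arm and no earlier censoring, turning one Day 28 event into a censoring lowers that arm's Kaplan-Meier healed proportion at Day 28 by 1/15, about 7 percentage points. The curve before Day 28 does not change.

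**The case against.** Several points on the other side stand.

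- The instruction only encourages, and a convenient date may well be 10 or more days after closure. The text permits a valid check; it does not steer towards one.
- A withdrawing patient who attends no check is censored as well. The instruction costs an event only where the patient would have come back at 10 days or later.
- A closed wound at 5 days does not show durable closure. The protocol anticipates reopening (Section 4.3.4), so censoring an early re-check is what the endpoint intends. The fault lies in the timing requested, not in the censoring rule.
- The Day 42 visit also collects examination, vital signs, laboratory, pain and adverse event data (7.5.2). In a first-in-human study an early exit visit has a safety purpose of its own.
- Section 4 has the Day 42 visit follow closure at some point between Day 14 and Day 28. If closure was first seen at an unscheduled visit in that period, the clock starts earlier and an early exit check may still qualify.

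Four stronger readings are tempting, and the documents do not support them.

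- A reader might infer that the exit check usually falls inside the 10 days. That needs a delay of 2 days or less with decisions spread evenly, or decisions concentrated early. The documents give no delay and no distribution of decisions.
- A reader might extend the point to withdrawal by Day 28, for instance closure on Day 10 and an exit check on Day 15. The request for an early date does not cover those patients, and the rule for them names no date.
- A reader might estimate the lost events from the 6 patients separating 36 from 30. Evaluable means per-protocol (10.1), and the measurement criterion in 10.2.1 is already met by a first 100% re-epithelialization or a completed Day 14 evaluation. Withdrawing after observed closure does not in itself make a patient non-evaluable, so that allowance says nothing about this group.
- A reader might put the cost at 1/30, about 3%, of the log-rank information per event. That average does not fit tied events at the last analysis time. As an illustration, take 4 versus 4 at risk, all closing on Day 28. The variance term d(n1n2/n²)(n − d)/(n − 1) is 8 × (16/64) × 0/7 = 0. Censoring one gives 7 × (16/64) × 1/7 = 0.25 and moves the score by 0.5.

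**Conclusion.** The point holds in a limited form. For patients first seen closed on Day 28 who decide to withdraw before Day 42, the plan asks for an exit check that can fall before about Day 38. Such a check cannot confirm closure under the plan's own event rule, and the patient is censored at the Day 28 visit. The inconsistency follows from the text alone; how often it arises does not. The 69% rests on a check held on the decision day and evenly spread decisions, and the share runs down to 0% as the delay reaches 9 days. On assumed healing and withdrawal rates, roughly 0 to 3 of 36 patients would be affected. It is a cheap improvement and does not threaten the primary analysis.

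**What to change.** In note 11 of the Schedule of Assessments and in Section 3.4, for patients withdrawing between Day 28 and Day 42 after a first 100% re-epithelialization, ask for the exit wound check on the first convenient date at least 10 days after that closure visit. Keep the immediate visit for anyone unwilling to return later.

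Section 10.2.2 needs no change for this: it already requires confirmation at least 10 days apart without tying it to a visit label.

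The cost is wording in two places and no extra visit. The downside is that a few patients who agree to the later date may not attend. Their exit safety assessments would then be lost along with the wound check, and the fallback does not cover that case.

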2. When DSW reaches 100% re-epithelialization by Day 14, a re-confirmation of wound closure will be performed on Day 28.										

3. Day 42 visit is only for patients whose DSWs do not reach to 100% re-epithelialization on Day 14 but heal on Day 28 as a re-confirmation.
4. For patients whose visit 8 (Day 42) is scheduled, these visits will be arranged at 90, 180, 270 and 360 days after visit 8 (Day 42); otherwise, these follow-ups will be planned at 90, 180, 270 and 360 days after visit 7 (Day 28). These long-term follow-ups should be scheduled even if 100% re-epithelialization is not observed on Day 28 or Day 42.
5. For treatment group: TWB-103+TegadermTM. For the control group: placebo+TegadermTM. The application will be discontinued when the 100% re-epithelialization of DSW is observed by the investigator.
6. The size of TegadermTM to be used for each patient will be determined by the investigator based on the size of DSW. Whenever TegadermTM falls off from DSW site, new TegadermTM should be applied immediately. If necessary, drainage is allowed, but re-application of TWB-103 or placebo is not necessary in this case.
7. TegadermTM is applied to the wound site after the investigator has finished the wound assessment if the DSW has not reached 100% re-epithelialization, regardless the original group assignment.
8. TegadermTM is dispensed to the patient regardless of the condition of DSWs. Patients are advised to apply TegadermTM to DSW site if the wound open remains or reappears, and to re-apply new TegadermTM every 2~3 days till next visit or wound closure. The amount of TegadermTM dispensed should be adequate for patient's use till next visit.
9. Unused TegadermTM is returned to the study site if TegadermTM is dispensed to the patient at the previous visit. Re-dispensing of unused TegadermTM to the same patient is allowed when the primary package of TegadermTM remains intact.
10. The patient will receive the application of TegadermTM on site for protection of wound site and/or start with other treatment recommended by the investigator if DSW does not reach 100% re-epithelialization by Day 28.

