16. At Visit 9~12, recording of 100% re-epithelialization and the area of target wound are not required. Instead, wound assessment will include scar assessment (Vancouver Scar Scale and if necessary, additional comments on scar elasticity, scar color and pigmentation), skin texture (relationship to surrounding skin, texture, margins, size and multiplicity) and any altered sensations.
17. Adverse events will start recording after signing informed consent.
18. At Visit 9~12, only TWB-103/placebo-relative and DSWs-relative adverse events will be recorded.

19. Randomization will be done before DSW creation but after all baseline procedures are completed and the subject has been deemed eligible for the study.
20. For Visit 2, the hematologic, biochemical and PRA tests conducted within 7 days prior to Day 0 are acceptable.
21. Patients should evaluate pain level at the (future) DSW site.
22. To prevent the itchiness and skin reaction caused by the long-term usage of TegadermTM, Vaseline Gauze or Non-Stick Gauze such as silastic foam dressings can be used on and after Day 14 at the investigator's discretion.
23. TegadermTM is dispensed only when Day 42 is scheduled. Unused TegadermTM should be returned on Day 42.

STUDY SCHEMA

*Note:

Day 42 visit is only for patients whose DSWs do not reach to 100% re-epithelialization on Day 14 but heal on Day 28 as a re-confirmation.

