7.5.2 Visit 8: Day 42 ± 3 days

(Only scheduled when the wound closure is not completed by Day14 but is observed on Day 28)

- Perform physical examinations
- Obtain vital signs

- Obtain blood samples for hemogram and biochemical tests
- Pain questionnaire
- Wound assessment
- Return unused Tegaderm™, Vaseline Gauze or Non-Stick Gauze
- Record adverse events
- Record concomitant treatments

7.5.3 Visit 9~12 (90, 180, 270, 360 days ± 14 days after Visit 7 (if no visit 8) or Visit 8)

- Perform physical examinations
- Obtain vital signs
- Pain questionnaire
- Wound assessment (scar assessment, skin texture and any altered sensations, see details in section 6.11)
- Record adverse events (only TWB-103/placebo-relative and DSWs-relative adverse events will be recorded)
- Exit of study (Visit 12)

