8.3 Collecting, Recording and Reporting of Adverse Events

8.3.1 Collecting and Reporting of AE

AEs may be volunteered spontaneously by the study subject, discovered as a result of general questioning by the study staff, or determined by physical examination. All AEs will be recorded on the CRF. For all AEs, the investigator must pursue and obtain adequate information both to determine the outcome of the AE and to assess whether it meets the criteria for classification as a serious AE requiring immediate notification. AEs should be reported starting from signing ICF to the end of study (Visit 12) or to the last visit patients finish before withdrawal. Follow-up of the AE, even after the date of study drug discontinuation, is required if the AE persists. The study subject will be followed until the event resolves or stabilizes at a level acceptable to the investigator.

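### Under the visit schedule, the time over which unrelated, non-serious adverse events are collected (to Day 28 or Day 42) depends on when the wound closes, and the between-arm comparison of AE incidence sets no common window

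*Combined protocol and SAP*

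**What the plan says.** Four sets of rules bear on this point.

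- **AE scope in long-term follow-up.** Schedule of Assessments, note 18: "At Visit 9~12, only TWB-103/placebo-relative and DSWs-relative adverse events will be recorded". Section 7.5.3 repeats the limit for the same visits: "Record adverse events (only TWB-103/placebo-relative and DSWs-relative adverse events will be recorded)".
- **Who has Visit 8.** Schedule note 3: "Day 42 visit is only for patients whose DSWs do not reach to 100% re-epithelialization on Day 14 but heal on Day 28". Section 7.5.2 agrees: "Only scheduled when the wound closure is not completed by Day14 but is observed on Day 28". At Visit 8, AEs are recorded without restriction, alongside a physical examination, vital signs, hemogram and biochemistry.
- **The general AE section.** Section 8.3.1 has all AEs entered on the CRF and gives a longer period with no limit by relatedness: "AEs should be reported starting from signing ICF to the end of study (Visit 12)", or to the last visit before withdrawal. Section 8.3.2 requires any hospitalization during participation to be reported as an SAE, except for social reasons or procedures planned before entry.
- **The analysis.** Secondary safety endpoint 2 (Section 2.2.2) is the incidence of AEs and SAEs. Section 10.2.2: "Incidence of AEs and SAEs will be analyzed by CMH test". Section 10.2.1 places it on the ITT population. No risk window, person-time measure or sensitivity analysis is given.

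**The concern.** A comparison of incidence assumes that patients in both arms are observed for events over the same period. Under note 18 and Section 7.5.3, the last scheduled visit with unrestricted AE recording is Visit 8 for some patients and Visit 7 for the rest. Time to closure, the primary efficacy outcome, decides which applies.

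An imbalance between arms is plausible. Section 1.1 expects donor sites to re-epithelialize in 7 to 21 days, which straddles the Day 14 cut-off. If TWB-103 moves closures from the Day 14–28 interval to before Day 14, fewer treated patients reach Visit 8. Their all-cause window is then shorter, and the product looks safer with no true difference. If it moves wounds from open at Day 28 to closed at Day 28, the bias runs against it. Visit 8 also adds laboratory tests, and clinically significant abnormalities count as AEs (Section 8.1), so detection rises as well as duration.

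**Working it through.** The plan gives no AE rate, healing rate or figure for AE observation time, so there is no figure of its own to reproduce. The windows below come from the documents. The rates and Visit 8 shares are assumptions.

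**1. Windows from Day 0 (visit schedule)**

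| Events | No Visit 8 | With Visit 8 | Ratio |
|---|---|---|---|
| Unrelated, non-donor-site AEs (note 18 and 7.5.3) | 28 days | 42 days | 42/28 = 1.50 |
| Product- or donor-site-related AEs | 28 + 360 = 388 days | 42 + 360 = 402 days | 402/388 = 1.04 |

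With the ±3-day visit windows, the first ratio ranges from 39/31 = 1.26 to 45/25 = 1.80.

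**2. Illustration with no true difference between arms**

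Assumptions: 40% of patients have an AE by Day 28 in both arms; the hazard is constant; Visit 8 is held in 2/15 TWB-103 and 7/15 control patients (15 per arm is the evaluable target in Section 3.1). Incidence is counted to Day 42.

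- With Visit 8, all events are recorded to Day 42: 1 − 0.6^1.5 = 0.535.
- Without Visit 8, unrelated non-donor-site events stop at Day 28 and the others continue. If a fraction *u* of the hazard is unrelated and non-donor-site, recorded incidence is 1 − 0.6^(1.5 − 0.5*u*).
- The artificial difference is (7/15 − 2/15) × [0.535 − incidence without Visit 8].

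Results:

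- *u* = 1 (all AEs unrelated and non-donor-site): incidence without Visit 8 is 0.400. The arms show 0.400 + 0.135 × 2/15 = 41.8% and 0.400 + 0.135 × 7/15 = 46.3%, a difference of 4.5 points.
- *u* = 0.5: incidence without Visit 8 is 1 − 0.6^1.25 = 0.472. The difference is (5/15) × (0.535 − 0.472) = 2.1 points.
- Hazard halved after Day 28, *u* = 1: incidence with Visit 8 is 1 − 0.6^1.25 = 0.472. The difference is (5/15) × (0.472 − 0.400) = 2.4 points.
- Hazard halved after Day 28, *u* = 0.5: (5/15) × [(1 − 0.6^1.25) − (1 − 0.6^1.125)] = (5/15) × (0.472 − 0.437) = 1.2 points.
- Equal Visit 8 shares: 0 points in every case.

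**3. Wider range and effect on the test**

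This check used 18 per arm (36 recruited), an exactly enumerated one-stratum CMH test at two-sided 0.05, and *u* = 1 throughout. For given rates and shares, *u* = 1 gives the largest difference. Day 28 incidence was 10% to 50%, Visit 8 shares were 20% v 50% or 20% v 80%, and the hazard after Day 28 was 1, 0.5 or 0.25 of the earlier one.

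- The artificial difference was 0.4 to 8.8 points.
- The rejection rate with no true difference was 0.035 to 0.100. With a common Day 28 window it was 0.033 to 0.065.
- In a middle case (30% by Day 28, shares 20% v 50%, constant hazard), recorded incidence was 32.3% v 35.7%. The rejection rate was 0.059, against 0.050 with the common window.

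**The case against.** The strongest objection is that the window is not settled. Section 8.3.1 read alone has every AE reported to Visit 12 for everyone, which gives 388 v 402 days and almost no problem. This stands as a conflict between passages, but it does not remove the point. Note 18 and Section 7.5.3 are the specific instructions for those visits, sites may follow either text, and Section 10.2.2 defines no window under either.

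A reader might infer that the whole AE and SAE comparison rests on 28 v 42 days. The documents do not support that:

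- **SAEs.** Section 8.3.2 requires hospitalizations to be reported throughout participation, whatever their cause.
- **Treatment-related events.** The Phase I primary endpoint and secondary safety endpoint 1 concern events that are recorded to Visit 12 in everyone.
- **Patients without Visit 8.** Day 28 is not a strict end for all of them. Unscheduled visits carry the Day 14 assessments, which include AEs. Wounds open at Day 28 are followed to closure with no AE scope stated for that follow-up. Patients withdrawing before Day 28 have the Day 28 assessments on leaving.

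It is also fair that the shares and rates are assumed, and that constant hazard is doubtful when the last application is at Visit 4 (Day 7). Even 4.5 points is only 0.045 × 15 = 0.7 of a patient in an arm of 15. All of this limits the size of the problem. The dependence on the efficacy outcome remains.

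**Conclusion.** The point holds for non-serious AEs unrelated to the product or the donor site, under note 18 and Section 7.5.3. Their scheduled collection runs to Day 42 in patients not closed by Day 14 but closed on Day 28, and to Day 28 in other completers. The CMH comparison of all-cause AE incidence therefore rests on a window set by the efficacy outcome.

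The effect is probably small and its direction is not known in advance. With the assumed 2/15 v 7/15 split, 40% incidence by Day 28 and constant hazard, it is about 2 points if half of AEs are of the affected type and 4.5 points if all are. It is less if the hazard falls after Day 28, and zero if the Visit 8 shares are equal. More extreme assumed shares and rates give larger figures, up to 8.8 points, but only if every AE is of the affected type. This is a worthwhile, inexpensive improvement to a secondary safety comparison and no threat to the primary endpoints.

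**What to change.** 1. Reconcile note 18 and Section 7.5.3 with Sections 8.3.1 and 8.3.2, and state the AE and SAE collection periods separately.
2. In Section 10.2.2 and the synopsis, compare all-cause AE incidence between arms over one window for every patient, from first application to the Day 28 visit. Starting at first application also keeps events recorded between consent and treatment (note 17: "Adverse events will start recording after signing informed consent") out of the comparison.
3. List all-cause AEs recorded after the Day 28 visit by arm, outside the CMH comparison.
4. Keep SAEs, and product- and donor-site-related AEs, over the full follow-up to Visit 12. They should not be cut at Day 28.

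The cost is a clarification of the collection rules and a sentence or two in Section 10.2.2 and the synopsis, with no added visits. With a common window, the artificial difference from Visit 8 is zero by construction. The downside is that all-cause non-serious AEs after Day 28 leave the comparative table, although they are still listed. That loss is modest if note 18 governs. It is larger if the reconciliation settles on the Section 8.3.1 period, because about 360 further days of such events would then be listed and not compared.
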